## Planned Analyses

**Primary Outcome:** Patient received a flu vaccine (yes/no) [Time Frame: At the 1 day visit]

**Question 1:** Do salient alerts indicating that patients are at high risk for flu and flu-related complications increase the likelihood that the patients will get vaccinated?

**Analysis 1 (Confirmatory):** We will test the hypothesis that patients whose clinicians were shown alerts with information about their risk status (patients randomized to the High-risk Alert or High-risk Alert with Risk Factors arms) will exhibit improved flu vaccination rates compared with patients in the Standard Alert arm.

For this analysis, we will run an OLS regression, including a binary predictor variable coding separately for baseline and the two High-risk Alert arms.

**Question 2:** Do alerts with information about a patient's factors that contribute to their high risk of flu and flu-related complications increase the likelihood that the patients will get vaccinated?

**Analysis 2 (Exploratory):** We hypothesize that patients whose providers were shown alerts with the factors that contributed to a patient's high risk (High-risk Alert with Risk Factors arm) will exhibit improved flu vaccination rates compared with patients in the arm with no risk factors (High-risk Alert arm).

For this analysis, we will run an OLS regression, including a binary predictor variable coding separately for each of the two High-risk Alert arms.

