## Analysis Notes

Analyses of the primary outcome will be limited to the first in-person appointment for each patient enrolled in the study. We will run a sensitivity analysis that includes patients who only attend telehealth appointments during the study.

Recent work suggests that OLS regressions are appropriate in randomized experiments with binary outcome variables such as ours (Gomila, 2021).

As the treatment variation is at the individual level, we will report heteroskedasticity-robust standard errors. We will also explore the impact of clustering these standard errors at the clinic and clinic-date levels to allow for dependence across observations within these clusters. We will also investigate heterogeneity across clinics that vary along characteristics of interest, including prior-year vaccination rates.

We may run additional robustness checks. These checks may include focusing on additional inclusion/exclusion criteria (e.g., including subsequent visits with alerts for a given patient) and subpopulations (e.g., different visit types).

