## Other Pre-specified Outcomes

Other Pre-specified Outcomes listed below include flu outcomes (diagnosis, complications) and COVID-19 vaccination. If there are any differences in these outcomes as a function of study

arm, the mechanism would almost certainly be increased flu vaccination. Therefore, we will only run analyses on Other Pre-specified Outcomes for analyses above where there is a significant difference in flu vaccination.

1. High confidence flu diagnosis

Patient received a flu diagnosis via a positive polymerase chain reaction [PCR]/antigen/molecular test (yes/no) during the 2022-23 flu season (from the patient's appointment date through April 30, 2023)

[Time Frame: Up to 8 months]

2. "Likely flu" diagnosis

Received a "high confidence flu" diagnosis (with positive polymerase chain reaction [PCR]/antigen/molecular test) and/or "likely flu" diagnosis (as assessed via International Classification of Disease [ICD] codes or Tamiflu administration or positive PCR/antigen/molecular test) (yes/no) during the 2022-23 flu season (from the patient's appointment date through April 30, 2023)

Note that "likely flu" is a superset of the "high confidence flu" diagnoses.

[Time Frame: Up to 8 months]

3. Flu complications

Diagnosed with flu-related complications (yes/no) during the 2022-23 flu season (from the patient's appointment date through April 30, 2023)

[Time Frame: Up to 8 months]

4. ER visits

Number of ER visits from the patient's message appointment date through July 31, 2023

[Time Frame: Up to 11 months]

5. Hospitalizations

Number of hospitalizations from the patient's message appointment date through July 31, 2023

[Time Frame: Up to 11 months]

6. COVID-19 vaccination rates

Received at least one COVID-19 vaccination (yes/no) during the 2022-23 flu season (from the patient's appointment date through April 30, 2023)

[Time Frame: Up to 8 months]

7. Flu vaccination during the 2022-2023 season

Patient receives a flu vaccine (yes/no) during the 2022-23 flu season (from the patient's appointment date through April 30, 2023)

[Time Frame: Up to 8 months]

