### **3. Number of appointments**

Patients may have more than one appointment scheduled during the study where the flu BPA fired. We will explore whether vaccination rates were higher with more appointments for those in the experimental groups compared to those in the control group with the same number of appointments.

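### Whole-season flu vaccination by randomized arm is analysed only if the first-visit result is significant, for a reason that does not apply to it

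*SAP*

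**What the plan says.** The primary outcome in the SAP (Planned Analyses) is flu vaccination, yes or no, with the time frame "Time Frame: At the 1 day visit". Analysis Notes adds: "Analyses of the primary outcome will be limited to the first in-person appointment for each patient enrolled in the study". Analysis 1 (confirmatory) compares the two high-risk alert arms together with the standard alert. Analysis 2 (exploratory) compares the two high-risk alert arms with each other.

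The section Other Pre-specified Outcomes lists seven items. It says of differences in them that "the mechanism would almost certainly be increased flu vaccination", and therefore that "we will only run analyses on Other Pre-specified Outcomes for analyses above where there is a significant difference in flu vaccination". Item 7 is defined as "Patient receives a flu vaccine (yes/no) during the 2022-23 flu season", counted from the appointment date through April 30, 2023. No exception is made for it. The sentence introducing the list mentions flu diagnosis, complications and COVID-19 vaccination, but not season-long flu vaccination.

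On later visits, Additional Exploratory Analyses (3. Number of appointments) notes: "Patients may have more than one appointment scheduled during the study where the flu BPA fired".

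**The concern.** The rationale is a mediation argument: if the alert did not change vaccination, it cannot have changed what follows from vaccination. Whatever one thinks of that for diagnoses or hospital visits, it has no bearing on item 7, which is the supposed mediator measured over a longer window. Applying the rule to item 7 treats a null at the first visit as a null for the season. The assigned alert can fire again at later visits, so the one does not follow from the other.

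If the first-visit test is not significant, the plan as written gives no season estimate by randomized arm. The report could not then say, from a planned analysis, whether later visits add to a small same-day effect or whether a small early difference disappears. The confirmatory first-visit comparison is not touched. What is lost is the estimate showing how far a null first-visit result extends to the season.

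**Working it through.** **Does anything else in the documents supply the season comparison?**

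- SAP, Analysis Notes: a check "including subsequent visits with alerts for a given patient" is named, but only as something that may be run.
- SAP, Number of appointments: experimental patients are "compared to those in the control group with the same number of appointments". That count arises after randomization, so this is not a comparison of the arms as randomized.
- SAP, the exploratory sections on age and sex, risk level, and department: these concern subgroups or interactions and name no season-long outcome.
- Protocol, Detailed Study Procedures: full-season data will still be examined if the primary time frame is shortened. This is conditional, and it defines neither an outcome nor an arm comparison.

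Item 7 is therefore the only committed and defined season comparison by arm.

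**Inputs.** SAP, Power Analysis: at least 20,000 per arm, 35% vs 36.34%, two-sided alpha .05, 80% power. Protocol, Recruitment and Enrollment: 90,000 patients. The 35% is taken as the first-visit rate because the primary outcome is measured there; the SAP gives it no time frame. The documents give no season rate or season effect, so both are assumed.

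**The plan's own figure.** With 20,000 per arm and pooled variance, power for 35% vs 36.34% is 79.9%. The stated 80% reproduces.

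**How often the condition fails.** SE = sqrt[p0(1−p0)/n0 + p1(1−p1)/n1]; P(significant) = 1 − Φ(1.96 − d/SE) + Φ(−1.96 − d/SE). Example for Analysis 1 at +0.5 points: SE = sqrt(.35×.65/20,000 + .355×.645/40,000) = 0.00414; d/SE = 1.21; P = 0.227, so item 7 is not run 77% of the time.

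| True first-visit gain (points) | Analysis 1, 20,000 vs 40,000 | Analysis 1, 30,000 vs 60,000 (90,000 in three equal arms, assumed) | Analysis 2, 20,000 vs 20,000 |
|---|---|---|---|
| 0.5 | 77% | 68% | 82% |
| 0.75 | 56% | 40% | 65% |
| 1.34 | 10% | 2% | 20% |

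The entries are the chance that item 7 is not run. If the first-visit base rate were 25% or 40% instead of 35%, the second column would read 73%, 49% and 6%, or 78%, 58% and 12%.

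**What that costs for the season comparison.** Analysis 1, 20,000 vs 40,000, season rate assumed 50%. Patients vaccinated at the first visit are a subset of those vaccinated in the season, so the two test statistics correlate at sqrt(.35×.50/(.50×.65)) = 0.73. The conditional figure is the bivariate normal probability that the first-visit test is significant and the season test is significant in favour of the alert.

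| First-visit effect | Season effect | Conditional | Unconditional |
|---|---|---|---|
| +0.5 | +0.25 | 7% | 8% |
| +0.5 | +0.5 | 13% | 21% |
| +0.75 | +0.75 | 31% | 41% |
| +0.5 | +1.0 | 22% | 64% |
| +0.75 | +1.0 | 40% | 64% |
| +1.34 | +1.34 | 83% | 87% |

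At a season rate of 40% or 60%, the +0.5/+1.0 row becomes 23% vs 65% or 21% vs 66%.

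**Precision of the estimate that would be lost.** 95% CI half-width for Analysis 1 = 1.96×sqrt(.25/20,000 + .25/40,000) = 0.85 points (0.83 at a 40% or 60% season rate). For Analysis 2 it is 1.96×sqrt(.25/20,000 + .25/20,000) = 0.98 points.

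**The case against.** Making lower-tier outcomes conditional on the primary is an ordinary choice, and here it is openly declared. Item 7 is last of seven, and the protocol does not name it among its additional outcomes. The large loss (64% to 22%) needs the effect to double after the first visit, and nothing in the documents quantifies such growth; the standard-alert arm also gets its alert at qualifying visits. The chance that the condition fails is not itself a measure of information lost. If controls catch up after a significant early lead, the condition has been met and item 7 is run, so that case is not harmed. Vaccination data will be collected in any event, and a season comparison could be reported as post hoc.

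Much of this stands. The power loss is modest when the season effect is no larger than the first-visit effect: at most about 10 points in the cases tabulated. The catch-up question is lost only when the early difference was too small to reach significance. For Analysis 2, already exploratory, less is at stake.

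It does not remove the point. The SAP's reason for the rule is the mechanism, not control of multiplicity, and the mechanism does not reach item 7. A post hoc season analysis would depart from the SAP's own statement that these outcomes are analysed only after significance. The value of a season estimate after a null is its confidence interval, not only its chance of significance.

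**Conclusion.** The concern holds. The SAP makes the only committed whole-season vaccination comparison by randomized arm conditional on a significant first-visit result, on a rationale that does not apply to it. The rule works contrast by contrast, so item 7 could be run for one question and not the other.

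The loss is small if the season effect does not exceed a small first-visit effect, or if the first-visit effect reaches the design target of 1.34 points. It is large only if the effect grows over later visits. Whatever the true effects, a null first-visit result leaves unplanned an estimate that would have a 95% CI of about ±0.85 points for Analysis 1. The figures rest on normal approximations, a 35% first-visit rate and an assumed 50% season rate; varying these rates as shown does not change the picture. The conclusion itself rests on the text. It should be corrected, but it does not threaten the confirmatory result.

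**What to change.** In the SAP, Other Pre-specified Outcomes, take item 7 out of the condition and state, for example: *Flu vaccination during the 2022–23 season (item 7) will be estimated by randomized arm with a 95% CI for Analyses 1 and 2 regardless of the first-visit result, labelled non-confirmatory, and reported beside the primary result.* The condition may stay for items 1 to 6.

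The cost is one sentence and one extra regression per question, on an outcome already listed. Sample size does not change. The downside is one more non-confirmatory estimate per question, which must be labelled as such.

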Geisinger introduces flu-related alerts on September 1st. As part of the research planning, randomization will occur in June 2022, in order to provide enough time to import risk scores and high-risk factors into Epic, so these data can be used to trigger the proper alerts. Because this intervention is timed to the 2022–23 flu season, the intervention period will begin ~9/1/22.

The primary outcome will be flu vaccination at the scheduled appointment, as recorded in the Geisinger EHR. We may limit the timeframe of the primary outcome to end earlier in the flu season (e.g., December), based on data suggesting that most patients get their flu shot by the end of the calendar year. If we choose this timeframe, we will still examine all data collected throughout the flu season. Additional outcomes to be measured between the patient's appointment and the end of the flu season will include: rates of flu diagnoses (both using the most rigorous biological tests, "high confidence flu", and using broader criteria that also include diagnosis codes and treatment information, "likely flu"), flu complications, and rates of other relevant healthcare utilization outcomes such as ER visits and hospitalizations. Finally, we will measure rates of COVID-19 vaccination in targeted patients.

Data Sources

All patients in this study will be in the top 20% of risk according to scores given by the Medial EarlySign flu algomarker. The development of this algorithm was already approved through a separate Geisinger IRB application (IRB number 2020-0211). Additionally, Geisinger deployed this system in a field study during the 2020–21 (IRB number 2020-0290) and 2021–22 flu seasons (IRB number 2021-0483) and contacted the identified patients with special messages (in addition to standard interventions conducted by the health system every flu season) to encourage vaccination.

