## Methods

Patients in the top 20% of risk for flu and complications, according to Medial's algorithm, were pre-randomized into the following arms:

1. Standard Alert: For flu-shot best-practice alert (BPA)-triggering appointments, the standard flu-shot BPA fires.
2. High-risk Alert: For BPA-triggering appointments, a modified BPA fires. This BPA includes salient features (e.g. larger alert headers, bold face, red font), and alerts the clinician that the patient is at high risk for flu and its complications.
3. High-risk Alert with Risk Factors: For BPA-triggering appointments, a modified BPA fires. This BPA includes salient features (e.g. larger alert headers, bold face, red font), and alerts the clinician that the patient is at high risk for flu and its complications. This BPA also presents the top factors contributing to the patient's high risk.

Patients are subsequently enrolled in the study if they attend at least one appointment where their assigned flu-shot BPA fired.

Clinicians are enrolled if they see a flu-shot BPA for an enrolled patient at a qualifying appointment.

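### The follow-up windows for flu diagnoses, complications, ER visits and hospitalizations open on the alert visit day, when vaccination cannot act and the alert itself might affect what is recorded

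*SAP*

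**What the plan says.** The SAP section Other Pre-specified Outcomes lists seven outcomes. Items 1-3 (high confidence flu, likely flu, flu complications) are counted "from the patient's appointment date through April 30, 2023". Items 4 and 5 use different wording and a later end date, but open on the same day: "Number of ER visits from the patient's message appointment date through July 31, 2023", with matching wording for hospitalizations. Items 6 and 7 (COVID-19 and flu vaccination) share the window of items 1-3. The protocol (Detailed Study Procedures) likewise measures these outcomes between the appointment and the end of the season.

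Neither document gives a lag, an exclusion of the visit day, a rule for flu already present at the visit, or a sensitivity analysis on the window start. Item 7 would naturally include a shot given at the visit, so the shared phrase is best read as including that day.

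Item 1 requires a positive test. Item 2 adds ICD "codes or Tamiflu administration" as qualifying evidence. Under Methods, each experimental alert "alerts the clinician that the patient is at high risk for flu and its complications". If these outcomes differ by arm, the SAP says, "the mechanism would almost certainly be increased flu vaccination". On that ground it analyses them only where flu vaccination differs significantly.

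**The concern.** On the visit day the vaccination route is closed: a shot given at the appointment cannot prevent an illness tested for, coded or treated at that appointment. Counting such events adds variance without information about the vaccine.

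A second route is open on that day. Tests, codes and Tamiflu orders follow from clinician decisions, and the clinician making them may be the one who has just read that the patient is at high risk. If the alert changes those decisions, same-day flu would differ by arm for a reason unrelated to vaccination. Extra testing or treatment in the high-risk arms would look like more flu there and would work against any protective effect. For items 4-5 the corresponding worry is a same-day ER referral or admission.

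What is at stake is the interpretation of secondary outcomes, in particular the vaccination-only reading. The primary outcome does not depend on these windows.

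**Working it through.** **The plan's own figure.** The SAP (Power Analysis) gives 80% power for 35% versus 36.34% with 20,000 per arm and two-tailed alpha .05. SE = sqrt[(0.35 x 0.65 + 0.3634 x 0.6366)/20,000] = 0.00479. Then 0.0134/0.00479 = 2.80, and power = Phi(2.80 - 1.96) = 79.9%. The figure reproduces (required n is 20,060 per arm), and the window start does not affect it.

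**Flu difference through vaccination.** Formula: rise in vaccination x flu risk after the visit x vaccine efficacy. The rise is 1.34 points (SAP, the detectable difference). The risk is 8% (protocol, Background, the US general population over a season). Efficacy is assumed.

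- Efficacy 100%: 0.0134 x 0.08 x 1.0 = 0.00107, about 11 per 10,000.
- Efficacy 40%: 0.0134 x 0.08 x 0.4 = 0.00043, about 4 per 10,000.
- With assumed risk of 1-8% and efficacy of 20-60%: 0.003 to 0.064 points, or about 1 to 26 cases per 40,000 patients in the two high-risk arms.

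**If the alert does not change same-day recording.** Assume 4% risk after the visit, 40% efficacy and 0.5% of patients with same-day flu, counted separately from later flu.

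- The difference is 0.0134 x 0.04 x 0.4 = 0.000214 with or without same-day events.
- The risk ratio moves from 1 - 0.000214/0.040 = 0.9946 to 1 - 0.000214/0.045 = 0.9952.
- The SE for 20,000 versus 40,000 moves from sqrt[0.04 x 0.96 x (1/20,000 + 1/40,000)] = 0.00170 to sqrt[0.045 x 0.955 x (1/20,000 + 1/40,000)] = 0.00180, about 6% wider.

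**If it does.** Formula: extra recorded flu = same-day frequency x relative rise in recording. Both inputs are assumed.

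- Frequency 0.1-1.0% and a 5% rise: 2 to 20 extra cases per 40,000. With a 10% rise: 4 to 40.
- Break-even in the 4%/40%/0.5% case: 0.000214/0.005 = 4.3%. A relative rise of that size offsets the whole vaccine effect of 8.6 cases per 40,000.
- Break-even is very sensitive to the inputs. At 8% risk, 60% efficacy and 0.1% same-day flu it is 64%. At 1% risk, 20% efficacy and 1% same-day flu it is 0.3%.

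**Power for such an effect.** At 8% risk, SE = sqrt[0.08 x 0.92 x (1/20,000 + 1/40,000)] = 0.235 points. A difference of 0.043 to 0.107 points is 0.18 to 0.46 SE, so two-sided power is about 5% to 7%.

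**The case against.** The strongest reply is that the bias is conjecture. All arms receive a flu-shot alert, the experimental ones add salience and a risk statement, and nothing in the documents says that this changes testing, coding or Tamiflu use. Without such an effect the difference estimated by OLS is unchanged. This stands. A reader might infer that the flu outcomes are biased and that a protective effect will be masked; the documents support neither the bias nor its direction. They give no same-day frequency and only part of the alert's trigger conditions. Alerts start around September 1 and also fire at specialty visits, where acute flu need not be the reason for attending.

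A reader might also take 11 per 10,000 as the most that vaccination could achieve. It is not: 1.34 points is a detectable difference, not a ceiling, and 8% is a general-population illness rate, not recorded flu in a cohort at high predicted risk. With 5-7% power for effects of this size, moving the window by one day is also unlikely to change a conclusion.

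Counting from exposure is a coherent way to estimate the total effect of the alert, and the mechanism sentence is hedged. That also stands, but it does not help the SAP's vaccination-only reading, because a total effect includes any direct route. Finally, a one-day shift leaves in illness already present but recorded later, and alert effects at later visits. So the shift is a partial remedy.

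**Conclusion.** The point holds as a small, inexpensive improvement. As written, the windows for items 1-5 include the visit day. Same-day events cannot be prevented by a shot given at that visit, so they contribute noise, and arm-dependent recording is possible on that day but not demonstrated. The vaccination-only premise is therefore least secure on the visit day.

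No size can be fixed for the same-day effect. The 4-11 per 10,000 rests on the SAP's detectable difference, the protocol's general-population rate and an assumed 40-100% efficacy. It shows only that the expected vaccine effect is small enough for modest differences in recording to matter to its interpretation. The calculation covers flu diagnoses; nothing comparable can be computed for complications, ER visits or hospitalizations. The primary analysis and its power are unaffected.

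**What to change.** - Start the windows for items 1-5 on the day after the index appointment. Date tests by order or collection, so that a visit-day test with a later result does not re-enter.
- Name the index appointment. The first-in-person rule in Analysis Notes is stated for the primary outcome only, and patients may have several alert visits.
- Keep the same-day start for items 6-7.
- Retain the window as written as a sensitivity analysis.
- Report same-day flu tests, flu codes and Tamiflu orders by arm. This turns the mechanism premise into something that can be checked.

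The cost is a few sentences in the SAP, a date filter and one table. A small number of events leaves the main analysis of these outcomes. The change does not remove events recorded later for illness already present, or alert effects at later visits, and the SAP should say so.
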